5.2.3.1 Management of Infusion Reactions

Infusion reactions have been observed following TRC105 administration, usually with the initial dose (including a grade 4 vasovagal reaction that resolved without sequelae), and were commonly associated with one or more of the following signs or symptoms: hypertension, hypotension, dyspnea, bronchospasm, chills/rigors, chills, sweats, fever, nausea, tachycardia, bradycardia, EKG changes, flushing, urticaria, pruritus, and headache, generally of grade 1 and 2 severity. Hypersensitivity reactions with infusions are a potential risk for sensitized patients, and TRC105 should be used with caution in patients with known hypersensitivity to any component of the drug product. Host anti-TRC105 antibodies to the murine or human portions of CHO-produced TRC105 are rare. In general, the risk of immunogenicity to therapeutic chimeric antibodies is small (<10%). The presence of HAMA or HACA neither correlated nor predicted the development of infusion reactions.

By extending the duration of the initial infusion from one to four hours and adding a glucocorticoid-based premedication regimen prior to each dose, the frequency and severity of infusion reactions were reduced. At dose levels where continuous TRC105 serum levels were achieved, with subsequent infusions dexamethasone was safely discontinued and the infusion duration reduced to one hour. **Table 5-10** provides guidelines for the definition and management of infusion related reactions.

To mitigate or avoid infusion reactions associated with TRC105, the following actions will be undertaken:

- a. The first dose of TRC105 will be split in two separate infusions to be infused over 4 hours each on days 1 (3 mg/kg) and 4 (12 mg/kg or 7 mg/kg if dose de-escalation occurs). If well tolerated, all subsequent infusions will be administered as a whole (i.e., 15 mg/kg or 10 mg/kg if dose de-escalation occurs) in their scheduled times and infusion time will gradually be reduced to 2 hours and then to a minimum of 90 minutes.
- b. The following TRC105 premedications should be administered 2 hours to 30 minutes prior to the start of each infusion:
 1. Acetaminophen 650 mg p.o. x 1
 2. Methylprednisolone 100 mg i.v.. In the absence of any infusion reaction with the prior dose, methylprednisolone may be discontinued beginning with cycle 3. In addition, methylprednisolone will be given in the case of a delay of ≥ 18 days between any two doses or if the patient develops an infusion reaction during the immediate prior infusion.
 3. Famotidine 20 mg i.v. or p.o. (or similar H2 blocker) x 1. Famotidine (or similar H2 blocker) may be discontinued starting with Cycle 2 in the absence of infusion reactions with the prior dose.
 4. Cetirizine 10 mg i.v. or p.o. x 1 (or similar oral or intravenous antihistamine). Cetirizine (or similar oral or intravenous antihistamine) may be discontinued starting with Cycle 2 in the absence of infusion reactions with the prior dose.
- c. During the first (day 1 and 4) infusion, vital signs should be checked every 30 minutes and methylprednisolone 100 mg IV should be readily available for infusion.

Table 5-10: Guidelines for the management of infusion related reactions

Grade	Signs or Symptoms	Recommended Action	Dose Adjustment or Modification
Grade 1 Mild transient reaction	Mild increase in heart rate but <100 bpm Mild increase in respiratory rate but <25 breaths per minute	Interruption not indicated Intervention not indicated	None
Grade 2 Infusion interruption indicated but responds promptly to symptomatic treatment	Increase in heart rate but <120 bpm Increase in respiratory rate but <30 breaths per minute Skin rash or mild pruritus	Withhold infusion until resolution of symptoms but no less than 30 minutes. Administer methylprednisolone 100 mg IV \pm diphenhydramine 50 mg IV.	None Premedications as per cycle 1. Do not shorten subsequent infusions until no infusion reactions are seen

		Resume infusion once symptoms resolve	
Grade 3 Prolonged recurrence of symptoms following initial improvement; hospitalization indicated	Increase in heart rate >120 bpm, palpitations and sense of “impending doom” Diffuse skin rash and pruritus Tachypnea >30 breaths per minute and mild wheezing	Interrupt infusion and do not resume. Administer methylprednisolone 250 mg IV and diphenhydramine 50 mg IV. Admit to the hospital for observation	None Escalate premedications to dexamethasone 8 mg PO BID in the day before and day of chemotherapy. Do not shorten subsequent infusions until no infusion reactions are seen. If the reaction recurs the patient will be taken off study.
Grade 4 Life-threatening consequences	Palpitations, tachycardia, dyspnea with stridor or wheezing, sense of “impending doom”, chest pain, diffuse rash with wheals and pruritus	Interrupt infusion and admit to the MICU Administer methylprednisolone 250 mg IV and diphenhydramine 50 mg IV. Administer pressors as indicated.	Do not rechallenge with TRC105. The patient will be taken off study.

5.2.3.3 Management of Anemia

Hypoproliferative anemia was the dose-limiting toxicity in the phase I study³⁵ and may be related to the action of TRC105 on proerythroblasts, the only cells in the bone marrow known to express high levels of CD105. When hemoglobin drops in a patient on the study, it is important to investigate for any ongoing blood loss. A reticulocyte count should be obtained to document the hypoproliferative nature of the anemia associated with TRC105. Anemia should be managed with standard supportive measures including transfusions of packed red blood cells if deemed necessary. If grade 3 or higher treatment related anemia develops, the dose of TRC105 should be reduced from 15 mg/kg to 10 mg/kg or held if the assigned dose is 10 mg/kg until resolution of the anemia.

5.2.3.4 Management of Headache

Headaches (grade 1 to 3) have been observed following TRC105 treatment, generally within hours following completion of the initial infusion. Headaches are throbbing in nature, have not been associated with radiographic abnormalities, and have responded to treatment with non-steroidal anti-inflammatory agents (including ketorolac) and to triptans. Extending the infusion to 4 hours or interrupting the infusion may also be tried to mitigate the headaches. Nasal congestion and periorbital edema have been observed with TRC105. The edema has been transient in nature and treated with corticosteroids. Antihistamines are useful for nasal congestion.

5.2.4 Goserelin

Description of the drug: Goserelin (Zoladex®) is a synthetic decapeptide analog of endogenous gonadotropin-releasing hormone. GnRH regulates follicle-stimulating hormone (FSH) and luteinizing hormone (LH) synthesis and secretion by the anterior pituitary gland, which in turn stimulates the production of estrogens by the ovary. In response to GnRH, FSH and LH synthesis initially increases, causing a transient increase in circulating levels of sex hormones. These hormones are however, regulated by feedback loops, so further hormone release is suppressed. Chronic administration of goserelin leads to sustained suppression of pituitary gonadotropins FSH and LH as the pituitary gland down-regulates and desensitizes GnRH receptors.

Pharmacodynamic properties: Within 3 weeks following initial administration of goserelin, serum estradiol is suppressed to levels similar to those observed in postmenopausal women. However, after suppression was attained, isolated elevations of estradiol were seen in up to 10% of the patients enrolled in clinical trials. Serum LH and FSH are suppressed to follicular phase levels within four weeks after initial administration of drug and are usually maintained at that range with continued use of goserelin. In 5% or less of women treated with goserelin, FSH and LH levels may not be suppressed to follicular phase levels on day 28 post treatment with a single 3.6 mg depot injection.

Pharmacokinetic properties: Goserelin in its depot formulation is released slowly initially for the first 8

days, and then there is more rapid and continuous release for the remainder of the 28-day dosing period. Despite the change in the releasing rate of goserelin, administration of goserelin every 28 days resulted in testosterone levels that were suppressed to and maintained in the range normally seen in surgically castrated men. When goserelin 3.6 mg depot was used for treating male and female patients with normal renal and hepatic function, there was no significant evidence of drug accumulation. However, in clinical trials the minimum serum levels of a few patients were increased. These levels can be attributed to interpatient variation. The apparent volumes of distribution determined after subcutaneous administration of 250 µg aqueous solution of goserelin was 20.3 liters for females. The plasma protein binding of goserelin obtained from one sample is 27.3%.

Metabolism of goserelin, by hydrolysis of the C-terminal amino acids, is the major clearance mechanism. All metabolites found in humans have also been found in toxicology species. Clearance of goserelin following subcutaneous administration of the solution formulation of goserelin is very rapid and occurs via a combination of hepatic metabolism and urinary excretion. More than 90% of a subcutaneous radiolabeled solution formulation dose of goserelin is excreted in urine. Approximately 20% of the dose in urine is accounted for by unchanged goserelin. (AstraZeneca, Package Insert).

Goserelin is generally safe to administer with other medications. Goserelin should be administered subcutaneously every 28 days into the anterior abdominal wall below the navel line using an aseptic technique under the supervision of a physician.

5.2.5 Concomitant Medications

The reason(s) for treatment dosage, and dates of treatment should be recorded in the source documents. Concomitant medications should be reported to the investigator and will be recorded as instructed in the study specific case report forms. Patients who experience TRC105-related temperature elevations or other infusion-related symptoms may be treated symptomatically with acetaminophen, dyphenhydramine, meperidine, or other medications as clinically indicated, including < 48 hours of treatment with corticosteroids. Patients should receive full supportive care, including transfusions, antibiotics, anti-emetics, etc. when appropriate. Pre-trial supportive care will continue. The following therapies are excluded during active protocol therapy: radiotherapy, hormonal therapy different from the agent prescribed in the protocol, cytotoxic chemotherapy, herbal medicines and cancer immunotherapy or other biologic agents.

If the patient is on low dose aspirin at baseline he/she may continue it if medically indicated. If the patient is on NSAIDs on study should also receive peptic ulcer disease (PUD) prophylaxis with an H2 or proton pump blocker.

Packed red blood cell, colony stimulating factors, and platelet transfusions should be administered as clinically indicated.

5.3 Dose Modifications and Delays

Dose modifications and delays are allowed. Determinations to reduce the dose, withhold, or delay the administration of a drug rely on the treating physician. The choice of the drug(s) (letrozole and/or everolimus and/or TRC105, or all three components) that need(s) to be withheld or dose reduced (everolimus or TRC105; delays but no dose reductions are allowed for letrozole) relies on the treating

physician and should be based on the nature of the observed adverse events. **The justification for dose modifications and delays should be clearly documented.** The maximum duration that a patient is allowed to withhold up to all three medications of the regimen is 7 days. Treatment can be resumed after 7 days at a lower dose level as outlined below for each individual component of the regimen. If treatment cannot be resumed within 7 days, the patient will be taken off study.

5.3.1 Dose modifications and delays with letrozole

Modifications. The dose of letrozole will not be modified (increased or decreased) in this protocol. Also letrozole cannot be substituted for another hormonal agent (e.g. anastrozole). Delays. The maximum duration that a patient is allowed to withhold letrozole due to adverse events is 7 days. If a patient cannot resume letrozole after 7 days or it is deemed necessary to withhold the medication again, the patient will be taken off study.

5.3.2 Dose modifications and delays with everolimus in phase II portion

Modifications. The dose for everolimus is 5 or 10 mg PO daily. In patients receiving 10 mg PO daily, dose reduction to 5 mg PO daily is allowed for adverse events or intolerance at the discretion of the treating physician. The reason for dose reduction must be clearly documented. Dose reductions at levels below 5 mg PO daily are allowed to 2.5 mg PO. No further reductions are allowed. Dose adjustments should be made if a patient's hepatic (Child-Pugh) status changes during treatment.

- Mild hepatic impairment (Child-Pugh A) – if the assigned dose was 5 or 10 mg PO daily, the recommended dose is 2.5 and 7.5 mg PO daily, respectively.
- Moderate hepatic impairment (Child-Pugh B) – if the assigned dose was 10 mg PO daily, the recommended dose is 5 mg daily. If the assigned dose was 5 mg PO daily, withhold everolimus until resolution of hepatic impairment and resume at 5 mg PO daily.
- Severe hepatic impairment (Child-Pugh C) – not recommended. If the desired benefit outweighs the risk, a dose of 2.5 mg daily must not be exceeded.

Delays. The maximum duration that a patient is allowed to withhold everolimus due to adverse events is 7 days. If a patient cannot resume everolimus after 7 days or it is deemed necessary to withhold the medication again, the patient will be taken off study.

5.3.3 Dose modifications and delays with TRC105

Modifications. The dose for TRC105 is 10 or 15 mg/kg IV every two weeks and it will be continued until 4 weeks prior to surgery. Dose reductions to 10 mg/kg due to adverse events are allowed and the justification(s) should be documented. Dose reductions below 10 mg/kg are not allowed and if deemed necessary, the patient will be taken off study.

Delays. All infusions of TRC105 should be administered within 3 days of the protocol-specified schedule. The maximum duration that a patient is allowed to withhold TRC105 due to adverse events is 14 days. If TRC105 is delayed > 3 days the first dose of TRC105 following the break needs to be split into two doses; 3 mg/kg should be given on the first day and the remainder of the dose (i.e., 12 mg/kg, or 7 mg/kg in the case of a dose de-escalation) will be given 3 days later and the

methylprednisolone dose should be reinstated. If a patient cannot resume TRC105 after 14 days or it is deemed necessary to withhold the medication again, the patient will be taken off study. Resumption at 10 mg/kg if the subject was receiving 15 mg/kg are allowed with the reinstatement of full premedication, as specified in Section 5.2.3.1.

5.3.4 Dose modifications and delays with goserelin

Modifications. No dose modifications are allowed with goserelin

Delays: delays up to 3 days are allowed to accommodate for scheduling issues, inclement weather, or other extraneous circumstances.

5.4 Study Procedures

5.4.1 Screening phase

Informed consent will be obtained before study-specific screening evaluations are performed. Screening evaluations must be performed within 4 weeks prior to day 0. Results of tests or examinations done as standard of care prior to obtaining informed consent and within 56 days prior to day 0 may be used rather than repeating tests.

The following evaluations and procedures will be performed during the screening phase:

- Signed informed consent.
- Clinical evaluations: medical history, demographics, weight and height, complete physical examination, vital signs and performance status.
- Determination of the surgical procedure to be performed at the time of diagnosis without the neoadjuvant treatment by the surgical oncologist in the multidisciplinary team. Determinations include unresectable (for locally advanced disease that cannot be adequately resected unless tumor shrinkage is achieved), mastectomy, and lumpectomy.
- Laboratory assessment: UA, CBC with differential and platelet count, serum chemistries (glucose, BUN, creatinine, total protein, albumin, bilirubin, calcium, alkaline phosphatase, AST, and ALT), serum electrolytes (Na, K, Cl), ferritin, and a lipid panel (cholesterol, triglycerides, HDL, and LDL) in a fasting state (at least 8 hours).
- Determination of menopausal status: FSH, LH, and estradiol levels.
- Pregnancy test in women with childbearing potential.
- Research biopsy (core needle biopsy of the tumor) (required).
- Sentinel lymph node biopsy if required.

- Estrogen and Progesterone receptor status.
- Her-2-neu by immunohistochemistry and or FISH (Negative: IHC 0, 1 or 2+ or non-amplified by FISH).
- Tumor assessments: Mammogram and breast ultrasound are required. PET/CT scan or CT scan of chest, abdomen, pelvis, with bone scan will be obtained. If the scan shows disease outside the breast and/or the axilla, the patient will not be enrolled in the trial.
- 12-lead EKG. Evaluation of the ejection fraction with an echocardiogram or MUGA, if clinically indicated.
- Concomitant medication assessment.
- Patients who have satisfied basic eligibility criteria will be assigned with a study patient number and the patient can proceed to be consented.
- Hepatitis B and C panels (see 5.2.2.3, table 5-2 and table 5-4 for Hepatitis B and C interpretation).

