Letrozole 2.5 mg PO daily, continuously until the day prior to surgery. TRC105 15 or 10 mg/kg IV every two weeks until 4 weeks prior to surgery. The first dose of TRC105 will be split into two doses; see Table 7-1 ([Study Calendar](#)) for additional details. Everolimus 5 or 10 mg PO daily, continuously until 4 weeks prior to surgery. Premenopausal women at the time of study enrollment will receive goserelin 3.6 mg subcutaneously q 4 weeks to achieve ovarian suppression.

Main Criteria for Inclusion/Exclusion:

Key Inclusion Criteria

- Recent diagnosis of hormone receptor positive and HER2 negative breast cancer.
- Stage 2 and 3 hormone receptor positive and HER2 negative breast cancer (stage T2-4 but not inflammatory, N0-2, M0).

- Histological grade I, II or III according to the modified Bloom Richardson scale⁵².
- No prior treatment specific for breast cancer.
- Menopausal status as defined by the National Comprehensive Cancer Network. Premenopausal women are eligible if ovarian suppression is achieved with goserelin
- ECOG performance status ≤ 2 (Karnofsky $\geq 60\%$).
- Must have signed study-specific informed consent.
- Liver Function Tests ≤ 2.5 times the upper normal limit (UNL).
- Staging workup: medical/surgical/radiation therapy evaluation, CT scans and bone scan.
- Lipid profile (cholesterol and triglycerides).
- ANC $\geq 1,500/\text{mm}^3$, platelets $\geq 100,000/\text{mm}^3$, Hemoglobin $\geq 10\text{g}\%$.
- Renal function: serum creatinine ≤ 1.5 institutional UNL or creatinine clearance $> 40 \text{ cc/min}$.

Key Exclusion Criteria

- Inflammatory breast cancer.
- Pregnancy.
- Metastatic disease.
- HER2 positive breast cancer by immunohistochemistry or FISH.
- Triple negative breast cancer (hormone receptor and Her2 negative).
- Disease that cannot be followed by imaging studies.

Safety Assessments:

- Vitals signs
- Weight
- ECOG performance status
- Hematology
- Chemistry
- Lipid profile
- Hepatitis panel
- Adverse events
- Concomitant medications

Efficacy Assessments:

- Physical examination
- Imaging studies (mammography, breast ultrasound, breast magnetic resonance imaging)
- Surgical Pathology

Other Assessments:

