3.2 Eligibility Criteria

Patients must have baseline evaluations performed prior to the first dose of study drug and must meet all inclusion and exclusion criteria. Results of all baseline evaluations, which assure that all inclusion and exclusion criteria have been satisfied must be reviewed by the Principal Investigator or his/her designee prior to enrollment of that patient. In addition, the patient must be thoroughly informed about all aspects of the study, including the study visit schedule and required evaluations and all regulatory requirements for informed consent. The written informed consent must be obtained from the patient prior to enrollment. The following criteria apply to all patients enrolled onto the study unless otherwise specified.

3.2.1 Newly diagnosed, histologically confirmed breast cancer.

3.2.2 hormone receptor positive and HER2 negative breast cancer^{12,58}; patients with Her2/neu positive tumors irrespective of their hormone receptor status will be excluded. At least 10% of tumor cell nuclei should be immunoreactive for hormone receptors (ER and/or PR) to be deemed eligible for the study¹⁰¹. Her2/neu negative is defined as¹⁰²:

- a. Immunohistochemistry (IHC) score of 0 (no staining is observed or membrane staining that is incomplete and is faint/barely perceptible and within $\leq 10\%$ of tumor cells) **OR**
- b. IHC score of 1 (incomplete membrane staining that is faint/barely perceptible and within $<10\%$ of tumor cells) **OR**
- c. Fluorescence *in situ* hybridization (FISH) HER2/CEP17 ratio of <1.8 or average HER2 gene copy number of <4 signals/nucleus for test systems without an internal control probe.
- d. Equivocal results for Her2/neu (defined as: IHC 2+ or FISH HER2/CEP17 ratio of 1.8-2.2 or average HER2 gene copy number 4-6 HER2 signals/nucleus for test systems without an internal control probe) should prompt reflex test (same specimen using an alternative method) or order a new test (new specimen if available, using IHC or FISH).

3.2.3 Histological grade I, II or III according to the modified Bloom Richardson scale⁵².

3.2.4 Stage at diagnosis T2 through T4a-c, N0 through N2, and M0. Patients with inflammatory breast cancer or metastatic disease at diagnosis will be excluded. Patients with multicentric, multifocal, and/or bilateral disease are allowed to participate so long as all tumors meet the histologic criteria of the study.

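### Section 5.4.1 counts HER2 IHC 2+ as negative without FISH, while section 3.2.2 treats it as equivocal and calls for a further test

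*Combined protocol and SAP*

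**What the plan says.** The combined protocol and SAP defines HER2-negative disease in two places.

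- **Section 5.4.1 (Screening phase)** lists, among the evaluations to be done: "Her-2-neu by immunohistochemistry and or FISH (Negative: IHC 0, 1 or 2+ or non-amplified by FISH". It gives no numerical limit for non-amplified and does not require FISH.
- **Section 3.2.2 (Eligibility Criteria)** has three routes to negative: (a) IHC 0, (b) IHC 1, or (c) FISH with a "HER2/CEP17 ratio of <1.8 or average HER2 gene copy number of <4 signals/nucleus". The copy-number limit is for test systems without an internal control probe. Item (d) covers what lies between: "Equivocal results for Her2/neu (defined as: IHC 2+ or FISH HER2/CEP17 ratio of 1.8-2.2", with a matching copy-number range. Such results "should prompt reflex test (same specimen using an alternative method) or order a new test", and the new test may be IHC or FISH.

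HER2-positive disease is barred three times. The synopsis lists "HER2 positive breast cancer by immunohistochemistry or FISH" as an exclusion, section 3.2.2 says that "patients with Her2/neu positive tumors irrespective of their hormone receptor status will be excluded", and section 3.3.2 repeats the exclusion.

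**The concern.** IHC 2+ is the score at which IHC alone does not settle HER2 status; section 3.2.2d says so by calling it equivocal. Section 5.4.1 removes that step by putting 2+ in the same group as 0 and 1. A coordinator working from the screening list could record an IHC 2+ tumour as negative and seek no further test.

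Two things are at stake. The first is the patient. Someone with an amplified tumour belongs to a group that the trial excludes. Section 5.2.5 does not allow other biologic agents during protocol therapy, so HER2-directed antibody treatment could be delayed.

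The second is the response estimate. The synopsis (Statistical Methods, item a) puts every enrolled patient in the final analysis, and no rule removes a patient later found ineligible. Phase II has 20 patients, and its first stage closes or continues on 0 versus at least 1 response in 10 (sections 4.2 and 10.1).

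**Working it through.** **Step 1: the two definitions side by side.**

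| Tumour result | Section 5.4.1 | Section 3.2.2 |
|---|---|---|
| IHC 0 or 1 | Negative | Negative (a, b) |
| IHC 2+, no FISH | Negative | Equivocal; reflex or new test (d) |
| IHC 2+, FISH below the 3.2.2c limits | Negative | Negative on FISH (c) |
| IHC 2+, FISH ratio 1.8-2.2 | Negative on the IHC limb | Equivocal; further test (d) |
| IHC 2+, FISH amplified | Negative on the IHC limb | Not negative |

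Rows 2, 4 and 5 differ. Row 5 is the one that matters most: the same patient is eligible under one section and excluded under the other.

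**Step 2: does other text settle which definition applies?** No clause ranks the two.

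- The exclusions in the synopsis and section 3.3.2 bar positive disease. A reader who takes 2+ as negative from 5.4.1 has nothing there that triggers FISH.
- Section 5.4.1 also lets standard-of-care results from the 56 days before day 0 stand in for new tests, so a diagnostic 2+ report can be carried forward.
- The on-study HER2 work in section 7.3.3 is by conventional IHC and would not show amplification.

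**Step 3: the stage 1 rule.** The plan's figure reproduces: at a true response rate of 20%, the probability of no response in 10 is 0.8^10 = 0.1074. Suppose one of the ten is misclassified.

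- If that patient cannot respond, the decision rests on nine eligible patients, and the probability of closing at a 20% rate is 0.8^9 = 0.1342.
- If that patient does respond, the study continues whatever the other nine show.

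One patient can therefore decide the stage, but the direction is not known.

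**Step 4: the final estimate.** One patient is 1/20 = 5 percentage points, and only if the outcome differs from that of the eligible patient who would otherwise have held the place. The plan's own 95% interval at an observed 20% is 5.7% to 43.6%, a width of 43.6 - 5.7 = 37.9 points.

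**Step 5: how many patients?** The documents give neither the share of tumours scored IHC 2+ nor the share of those amplified. Assume 15-25% and 10-25%:

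- low: 0.15 x 0.10 = 0.015; 0.015 x 20 = 0.3 patients
- high: 0.25 x 0.25 = 0.0625; 0.0625 x 20 = 1.25 patients

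This further assumes that no IHC 2+ tumour has a second test, that every amplified one is enrolled, and that shares among screened tumours carry over to enrolled patients. It should be read only as an assumed upper bound; any second testing lowers it.

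**The case against.** The strongest reply is that section 3 governs in practice. Section 3.2 requires every patient to satisfy all inclusion and exclusion criteria and has the principal investigator or a designee review the baseline results before enrolment. Section 5.1 has a separate office check the criteria at registration, section 9 requires eligibility to be confirmed before therapy, and the Study Calendar (Table 7-1) carries its own inclusion/exclusion item at screening. Section 5.4.1 is a list of procedures, and nothing calls it the eligibility checklist. For an amplified patient to enter, both the investigator review and the registration check would have to use a parenthesis from that list instead of the criteria.

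Most of this stands. It makes wrongful enrolment a possibility, not an expectation. It does not remove the conflicting definition, and neither check is told which HER2 definition to use.

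A reader might also infer more than the documents support:

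- **That 3.2.2 already requires FISH for every 2+ tumour.** It says such a result should prompt a reflex or a new test, and the new test may be IHC. A repeat IHC of 0 or 1 would qualify.
- **That the printed IHC descriptions in 3.2.2a and 3.2.2b add to the problem.** As printed, scores 0 and 1 overlap and faint staining above 10% of cells has no category. Both scores are negative, so the overlap changes nobody's eligibility, and the gap does not admit a HER2-positive patient by the IHC route. A misread inequality sign is possible. This is not a ground for the point.
- **That HER2-directed care would be withheld.** Neoadjuvant therapy is capped at 24 weeks, followed by surgery and adjuvant therapy by standard of care or physician discretion (section 4.3). Section 4.7 diverts some patients sooner. A delay over treatment and the time to surgery is the most that can be claimed.

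**Conclusion.** The inconsistency is real and concerns a core entry criterion. Read literally, 5.4.1 admits IHC 2+ without FISH; 3.2.2 does not; no text ranks them. A HER2-amplified patient could therefore enter if staff apply 5.4.1, subject to the checks in sections 3.2, 5.1 and 9.

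The size cannot be derived from the documents. The range of 0.3 to 1.25 of 20 patients rests wholly on the assumed rates and on no second testing. The effect on the response rate is at most 5 points per patient in the final 20, in an unknown direction, on a secondary and descriptive endpoint. The stage 1 decision is more sensitive, because a single response changes it. The contradiction holds whatever the rates. It should be corrected, mainly because the correction is simple and protects patients as well as the estimate.

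**What to change.** Replace the parenthesis in section 5.4.1 with: *Negative as defined in 3.2.2; equivocal results, including IHC 2+, must be resolved as described in 3.2.2d before enrolment.* This leaves one definition, supplies the FISH limits that 5.4.1 lacks, and keeps both the reflex and the new-test routes. A FISH-only condition should not be added, because it would be stricter than 3.2.2d and create a fresh conflict.

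While the text is open, the sponsor could state in 3.2.2d what follows if the repeat result is again equivocal, which it does not now say, and check the inequality signs in 3.2.2a and 3.2.2b against the source.

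The cost is a written amendment with IRB approval (section 11.1). The follow-up test is already called for in 3.2.2d. The only tightening is that 'should prompt' becomes resolution before enrolment, which fits the section 3.2 requirement that criteria be reviewed as met before a patient is enrolled. Sample size and analysis are unchanged.

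### Section 5.4.1 counts HER2 IHC 2+ as negative, Section 3.2.2d counts it as equivocal and asks for another test, and nothing says which governs

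*Combined protocol and SAP*

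**What the plan says.** Section 5.4.1 (Screening phase) lists the procedures done before entry. Its HER2 item is "Her-2-neu by immunohistochemistry and or FISH (Negative: IHC 0, 1 or 2+ or non-amplified by FISH". Testing may be by IHC, FISH or both, and the routes to a negative result are joined by 'or'.

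Section 3.2.2 (Eligibility Criteria) accepts three results as negative: IHC 0, IHC 1, or a FISH result below the cut-offs (ratio under 1.8, or fewer than 4 copies per nucleus where there is no control probe). Item d is separate: "Equivocal results for Her2/neu (defined as: IHC 2+ or FISH HER2/CEP17 ratio of 1.8-2.2", with a matching copy-number range. Such a result "should prompt reflex test (same specimen using an alternative method) or order a new test (new specimen if available, using IHC or FISH".

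The HER2-positive exclusion appears in three places. Section 3.2.2 says "patients with Her2/neu positive tumors irrespective of their hormone receptor status will be excluded", Section 3.3.2 repeats the exclusion with a literature citation in place of a definition, and the synopsis excludes "HER2 positive breast cancer by immunohistochemistry or FISH". Section 3.2 adds that patients "must meet all inclusion and exclusion criteria".

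**The concern.** HER2-negative status defines the trial population in the objectives, in Section 3.1 and in Section 4. The two places that tell a site how to establish it disagree on one common type of result. Section 5.4.1 is also the only procedural instruction on HER2 testing: the study calendar (Table 7-1) has no HER2 row and refers the reader back to Section 5.4.

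What is at stake is whether the enrolled population is the one the trial describes. The protocol itself says that response to neoadjuvant therapy depends on molecular subtype (synopsis Background; Section 2.1.1). The synopsis (Statistical Methods, item a) includes all enrolled patients in the final analysis, so a patient admitted on an unresolved HER2 result would still count. Phase II has 20 patients, and its only early look is after 10.

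**Working it through.** **Step 1: the two definitions, case by case.**

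| Test result | Section 5.4.1 | Section 3.2.2 |
|---|---|---|
| IHC 0 or 1 | Negative | Negative (a, b) |
| IHC 2+, FISH ratio below 1.8 | Negative | Negative (c) |
| IHC 2+, no FISH | Negative | Equivocal; another test called for (d) |
| IHC 2+, FISH amplified | Negative on the literal 'or' | Not negative; also barred by the HER2-positive exclusions |

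The sections agree in the first two rows and disagree in the last two. The fourth row is blocked in practice, because a tumour known to be amplified is excluded in three places. The third row is the live one: without a second test nobody knows whether the tumour is amplified, so the HER2-positive exclusions have nothing to act on.

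**Step 2: how many patients?** The documents give neither the share of tumours that are IHC 2+ nor the share of those that are amplified, so no number can be derived. For scale only, assume:

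- 10% to 20% of tumours are IHC 2+;
- 10% to 25% of those are amplified;
- no IHC 2+ tumour is ever retested, i.e. 3.2.2d is ignored every time.

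The third assumption makes this a worst case for the assumed frequencies.

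- Share of enrolled patients with an amplified tumour: 0.10 × 0.10 = 0.01 to 0.20 × 0.25 = 0.05.
- Expected number: 0.2 to 1.0 of 20 in phase II; 0.4 to 1.9 of 38, the top of the planned 26 to 38 in Section 4.3.
- Chance of at least one of 20: 1 − 0.99^20 = 0.18 to 1 − 0.95^20 = 0.64.
- Chance of at least one of 38: 1 − 0.99^38 = 0.32 to 1 − 0.95^38 = 0.86.

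Any retesting lowers all of these.

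**Step 3: effect on the response rate.** Add the unfavourable assumption, which the documents do not support either way, that amplified tumours never respond. At a true rate of 20% in the others:

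- Overall rate: 0.20 × 0.99 = 19.8% to 0.20 × 0.95 = 19.0%.
- One such patient among 20 changes the rate by at most 1/20 = 5 points, and only if the patient displaced would have responded. The expected change is 0.20 × 5 = 1 point.
- For comparison, Section 10.1 gives a 95% interval of 5.7% to 43.6% at an observed 20%.

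**Step 4: effect on the stage 1 look.**

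- Plan's own figure: 0.8^10 = 0.1074, which matches Section 10.1 and Table 10.1.
- At 19.8%: 0.802^10 = 0.110. At 19.0%: 0.81^10 = 0.122.
- With exactly one certain non-responder among the ten: 0.8^9 = 0.134.

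**The case against.** The strongest reply is that Section 5.4.1 is a checklist and Section 3 sets eligibility. Section 3.2 requires every criterion to be met and the results to be reviewed before enrolment. Section 5.1 has the registering office verify the criteria in real time, and Section 9 requires eligibility to be confirmed before therapy. On this view an unresolved IHC 2+ tumour gets in only if both the site and the office overlook 3.2.2d, and the bracket in 5.4.1 may be loose shorthand for 2+ that is non-amplified.

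Much of this stands. The safeguards are real, and they bar any tumour known to be amplified. They do not close the gap, because whoever verifies eligibility holds the same two definitions with no rule of precedence, and the bracket says 'or'.

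Some stronger readings are tempting and should be resisted:

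- *That an IHC 2+ tumour fails 3.2.2.* It does not; its status is open until another test is done.
- *That a known share of enrolled patients would be amplified.* The documents give no rates, and the figures above assume that 3.2.2d is never followed.
- *That such patients would not respond and would dilute the result.* The documents say that response varies by subtype, but not how amplified tumours respond to this regimen.
- *That they would spend 24 weeks on treatment.* Section 4.7 diverts patients with progression at any time, or stable disease after 4 cycles, so a patient without response would be expected to leave by about week 16.

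**Conclusion.** The contradiction is in the current operative text and can be confirmed by reading Sections 3.2.2 and 5.4.1 together. It concerns a criterion that defines the population, and it leaves one route open: an IHC 2+ tumour enrolled on IHC alone with its amplification status unknown. That conclusion needs no assumption about frequencies.

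The size of the consequence cannot be derived from the documents. Even with the assumed frequencies, no retesting and no response in amplified tumours, the expected effect is about 0.2 to 1 percentage point on a 20% rate and 0.003 to 0.015 on the 0/10 probability. Both are small next to the planned precision, and efficacy is a secondary, descriptive endpoint. The reason to correct it is that eligibility should have one definition; the documents do not support a claim that the efficacy estimate would be materially biased. It should be corrected, and it does not call the design into question.

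**What to change.** Reconcile the two sections by replacing the bracket in 5.4.1 with a cross-reference, for example: *Negative: as defined in 3.2.2; equivocal results, including IHC 2+, are to be resolved per 3.2.2d before enrolment.*

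The wording should not name a particular retest. Section 3.2.2d allows either an alternative method on the same specimen or a new test by IHC or FISH, and requiring a negative FISH would add a rule that the protocol does not contain.

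Two neighbouring gaps can be dealt with in the same edit. Section 5.4.1 gives no cut-off for a non-amplified FISH result, while 3.2.2d treats ratios of 1.8 to 2.2 as equivocal; the cross-reference settles this. Section 3.2.2d does not say how to class a tumour that is still equivocal after the repeat test; the sponsor should state this.

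The cost is one line of protocol wording for the main change, and no test is added beyond what 3.2.2d already calls for.
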